12.5.3 Pharmacokinetics

Only cipargamin pharmacokinetics will be determined in this study. For each cohort, cipargamin plasma concentration data will be listed by cohort, treatment, participant, and visit/sampling time point. Descriptive summary statistics will be provided by cohort (including pooled cohort), treatment and visit/sampling time point, including the frequency (n, %) of concentrations below the LLOQ and reported as zero.

Summary statistics will include mean (arithmetic and geometric), SD, CV (arithmetic and geometric), median, minimum and maximum. Concentrations below LLOQ will be treated as zero in summary statistics and for PK parameter calculations. For geometric related mean and CV, concentrations below LLOQ will be included as half of the LLOQ value.

Table 12-4 Non-compartmental pharmacokinetic parameters

AUClast	The AUC from time zero to the last measurable concentration sampling time (tlast) (mass x time x volume-1)
AUCinf	The AUC from time zero to infinity (mass x time x volume-1)
AUC0-t	The AUC from time zero to time t (e.g. 24h) (amount x time x volume-1)
Cmax	The maximum (peak) observed plasma, blood, serum, or other body fluid drug concentration after single dose administration (mass x volume-1)
Ct	Concentration at time t (mass x volume-1)
Tmax	The time to reach maximum (peak) plasma, blood, serum, or other body fluid drug concentration after single dose administration (time)
T1/2	The elimination half-life associated with the terminal slope (λ_z) of a semi logarithmic concentration-time curve (time).
CL/F	The total body clearance of drug from the plasma (volume x time-1)
Vz/F	The apparent volume of distribution during terminal phase (associated with λ_z) (volume)

Pharmacokinetic variables:

The following pharmacokinetic parameters will be determined using non-compartmental method(s) for IV cipargamin:

AUC_{inf}, AUC_{0-t}, C_{max}, C_{2min}, T_{max}, T_{1/2}, CL, and Vz.

Bio-fluid concentrations will be expressed in mass per volume units. All concentrations below the limit of quantitation or missing data will be reported as such in the concentration data listings. Concentrations below the limit of quantitation will be treated as zero in summary statistics.

The pharmacokinetic parameters will also be listed by cohort, treatment and participant.

12.5.4 CCI

CCI

12.5.5 CCI

CCI

12.6 Analysis of exploratory endpoints and assessments

CCI

CCI

A large, bold, red watermark consisting of the letters 'CCI' is positioned in the upper left quadrant of the page. The background of the page is a solid dark grey or black, which makes the red text stand out prominently. The letters are slightly stylized, with the 'C's having a modern, rounded appearance and the 'I' being a simple vertical bar.

12.7 Interim assessment

An interim assessment (IA) after Cohort 2 will be conducted to decide upon the dosing regimen for Cohorts 3-5. All randomized participants in Cohorts 1-2 with key efficacy, safety and PK data up to Day 29 will be included in this IA.

An independent Data Monitoring Committee (DMC) will review participant safety at several time points during the study. If notable adverse events or safety concerns are found at one of the planned dose levels, the DMC may recommend dose and/or age adjustment, stopping a cohort or the study early for safety reasons.

An additional IA may be conducted (for e.g. after Cohort 4) to support decision making concerning the current clinical study, the sponsor's clinical development projects in general or in case of any safety concerns.

The clinical team may be communicated interim results (e.g. information needed for planning/modifying another study) to relevant Novartis teams for information, consulting and/or decision purposes.

12.8 Sample size calculation

12.8.1 Primary estimand

The primary objective is to show that an IV cipargamin dose regimen is non-inferior to the IV artesunate in proportion of participants with $\geq 90\%$ *P. falciparum* parasite reduction at 12 hours for each cohort. In the artesunate Phase III studies SEAQUAMAT (Dondorp et al 2005) and AQUAMAT (Dondorp et al 2010), proportion of participants with $\geq 90\%$ *P. falciparum* parasite reduction was not reported for both artesunate and quinine. Therefore, a non-inferiority margin in proportion of participants with $\geq 90\%$ parasite reduction for IV cipargamin vs IV artesunate cannot be derived statistically based on historical data. A non-inferiority margin of 10% is set based on clinical judgement. The KM plot for time to $> 90\%$ parasite clearance by Kremsner et al (2016) indicated that the proportion of participants with 90% parasite reduction at 12 hours was about 50%, 45%, and 40% for artesunate 3 dose IM (n=341), 3 dose IV (n=337), and 5 dose IM (n=333), respectively. Therefore, we assume that the

CCI

Based on these assumptions, a sample size of 13 participants per treatment group will provide 90% power to show that a cipargamin treatment group is non-inferior to artesunate for each cohort in the proportion of participants with $\geq 90\%$ *P. falciparum* parasite reduction at 12 hours using a non-inferiority margin of 10% absolute difference at the 1-sided 5% significance level (nQuery 7.0 Table PTE1a). Considering that 5% of participants that may be excluded from the analysis (Kremsner et al (2016)), at least 14 participants will be randomized to each treatment arm in each cohort except Cohort 1 to achieve 13 evaluable participants per arm for the primary analysis. The sample size for Cohort 1 will be 6 participants in each arm, which is not based on the statistical justification (no formal testing will be performed in this Cohort 1) but based on clinical judgment to rule out the risk of any potential untoward safety or lack of efficacy issues in this small group of moderately severe malaria participants before enrolling the severe malaria participants into the study.

12.8.2 Secondary endpoint(s)

Secondary estimand of clinical success at 48 hours:

The key secondary estimand of clinical success at 48 hours may be used as a primary efficacy endpoint for the Ph.3 study. The key secondary objective is to estimate clinical success rates for cipargamin and artesunate individually as well as the difference between two treatment groups at 48 hours with good precision. The cipargamin treatment group for this estimation will

[figure not shown]
be the one, which is used in all the cohorts across the study; participants from this treatment group will be pooled from all Cohorts. Similarly, for the artesunate group, participants will be pooled from all Cohorts.

The sample size calculation considers the precision of the estimates for the individual treatment groups as well as the difference between the two treatment groups; and the precision is measured in the form of half width of the associated 90% CI as mentioned below.

Precision of the estimates of single proportion

For a binary endpoint, let X be a number of clinical successes with n participants, X follows a binomial distribution $Bin(n, p)$ where p is the true proportion of participants with clinical success for a treatment group at a visit. Proportion (p) is estimated by X/n with a 90% CI based on the exact method; and the half-width of 90% CI is considered as the precision of the estimate. Consider d as the targeted half width of CI and P_l and P_u as lower and upper limits of 90% CI based on X and n (exact method), the probability that the observed half width ($0.5[P_u - P_l]$) is at most the targeted half, ie., $\Pr\{0.5(P_u - P_l) \leq d | Bin(n, p)\}$ will be used to justify the sample size for a single proportion.

Figure 12-1 Plot of probability that half width of 2-sided 90% CIs for a single proportion is at most 0.1 for various true proportions

Generated using R 3.4.3

For designated half width d , the sample size, n is chosen so that the probability that the half width of 2-sided exact 90% CI for p is at most d is at least 80% at a likely true p .

Figure 12-1 displays the probabilities that the half width of 2-sided exact 90% CIs for a single proportion ≤ 0.1 for true proportions of 0.5 to 0.9 by 0.1. To maintain the same probability, such as 80% represented in the horizontal dash line, the sample size is higher when the true proportion is closer to 0.5 and is lower when it is away from the 0.5. For instance, when $p=0.5$, $n=76$ is required to estimate the true proportion with at least 80% probability that the half width of 2-sided exact 90% CI is $\leq 10\%$. Similarly, when $p=0.7$, $n=70$ is required to estimate the true proportion with at least 80% probability that the half width of 2-sided exact 90% CI is $\leq 10\%$.

Precision of the estimates of difference between two proportions

For estimating the difference between two proportions, the half width of 2-sided 90% CIs calculated using Wilson's uncorrected method is considered as the precision of the estimation. The probability that the half width of 2-sided 90% CI for difference between 2 proportions is at most a targeted width (d) at likely proportions will be considered for the sample size selection.

Figure 12-2 displays the probability that the half width of Wilson's uncorrected 2-sided 90% CIs for the difference between 2 proportions is most 0.1 for true equal proportions of 0.5, 0.6, 0.7, 0.75, 0.8, and 0.9. To maintain the same probability, such as 80% represented in the horizontal dash line, the sample size is higher when the two equal true proportions are closer to 0.5. For instance, when $p=0.5$ for both treatment groups, $n=133$ is required in order to have at least 80% probability that the half width of 2-sided 90% CIs for the difference is at most 0.1. Similarly, when $p=0.75$ for both treatment groups, $n=107$ is required in order to have at least 80% probability that the half width of 2-sided 90% CI for the difference is at most 0.1.

Compared with Figure 12-1, Figure 12-2 shows that the required sample size for the precision in estimating the difference between 2 proportions is higher than the corresponding sample size required for the precision in estimating a single proportion. Therefore, the sample size for the study will be justified based on the half width of 2-sided 90% CIs for the difference between 2 proportions.

[figure not shown]
The proportion of participants who were alive without new/worsening complication at the end of study for artesunate was 0.679 in SEQUAMAT and 0.791 in AQUAMAT (private communication). Therefore, it is estimated that the proportion of participants meeting the proposed clinical endpoint is about 0.75 in the artesunate arm. To date, cipargamin has not been tested in patients with severe malaria. It is assumed that the proportion in the cipargamin arm would be same as that of artesunate.

From Figure 12-2, a sample size of $n=107$ per arm is required in order to have at least 80% probability that the half width of 2-sided 90% CIs for the difference between 2 proportions is at most 0.1 if the true proportion is 0.75 for both treatment groups. As participants treated with the same treatment from all cohorts will be pooled together for the analysis using the FAS, this sample size is considered for the artesunate and the cipargamin dose regimen that is used in all cohorts.

Taking account that about 8% participants may be excluded from the FAS, participants from all cohorts will be randomized to yield about 116 randomized each for the artesunate and the cipargamin dose regimen that is used in all cohorts so that 107 participants per group are evaluable for this analysis. The enrollment may be increased if the number of participants excluded from the FAS is higher. Considering the required sample size for each cohort for the

primary endpoint (see [Section 12.8.1](#)) and the potential participant population available for recruitment, the 116 randomized for a treatment group will split into 6 participants for Cohort 1, 14 participants for Cohort 2, 38 participants for Cohorts 3 and 4, and 20 participants for Cohort 5.

Figure 12-2 Plot of probability that half width of 2-sided 90% CIs for 2 proportion difference is at most 0.1 for various true equal proportions

Generated using R 3.4.3.

Safety events

[figure not shown]
Safety events will be evaluated using the safety set, which is expected to be similar to the randomized set. Occurrence of a safety event for a regimen (cipargamin or artesunate) will be evaluated by cohort and overall with all participants pooled from all cohorts. The probability of observing selected minimal number of events is displayed in [Figure 12-3](#) by sample size. From this plot,

- for a treatment group in a cohort with 6 participants, the probability of observing at least 2 events is $> 75\%$ if true event rate is $\geq 40\%$ but $< 20\%$ if true event rate is $\leq 10\%$
- for a treatment group in a cohort with 14 participants, the probability of observing at least 2 events is about 80% if the true event rate is $\geq 20\%$ but $< 20\%$ if the true event rate is $\leq 5\%$;

- for a treatment group in a cohort with 20 participants, the probability of observing at least 3 events is about 80% if the true event rate is $\geq 20\%$ but $< 20\%$ if the true event rate is $\leq 7\%$
- for a treatment group in a cohort with 38 participants, the probability of observing at least 9 events is about 80% if the true event rate is $\geq 20\%$ but $< 20\%$ if the true event rate is $\leq 10\%$
- for a regimen that is selected for Cohorts 3-5 with 116 participants, the probability of observing at least 14 events is $> 80\%$ if the true event rate is $\geq 15\%$ but $< 20\%$ if the true event rate is $\leq 9\%$.

The minimal number of events mentioned above may be used a guidance to interpret the occurrence of safety events in a treatment group in a cohort or pooled cohorts.

Figure 12-3 **Probability of observing selected minimal number of events by sample size**

Generated using R 3.4.3

13 Ethical considerations and administrative procedures

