2.2 Secondary estimands

The secondary clinical question of interest is: What is the difference between IV cipargamin and IV artesunate in clinical success at 48 hours without the need of IV rescue antimalarial medication?

[figure not shown]
The justification for the secondary estimand is that it will reflect the clinical outcome including recovery from the most severe symptoms of the disease with IV treatment before earliest possible administration of oral antimalarial medication at 48 hours. This objective is being evaluated for possible use in Phase III study. Further details can be found in [Section 12](#).

The secondary estimand is described by the following attributes:

1. Population: participants with severe *P. falciparum* malaria and treated with at least one dose of IV study medication. Further details about the population are provided in [Section 5](#).
2. Variable: A binary outcome indicating clinical success- participant is alive and has absence of asexual parasites and no critical signs of severe malaria (See [Section 8.3.1.2](#) for further details) at 48 hours.
3. Treatment of interest: IV cipargamin vs IV artesunate. Further details about cipargamin and artesunate are provided in [Section 6](#).
4. Intercurrent event: receive IV rescue antimalarial medication before assessing the clinical success prior to H48.
5. Summary measure: Proportion of participants with clinical success with 90% CI within a treatment group as well as the difference between the cipargamin and artesunate treatment group.

3 Study design

Figure 3-1 Study design

Notes:

KAE609 (Cipargamin)

Moderately severe malaria – Prostration and/or repeated vomiting (Barnes et al 2004)

Study to progress from Cohort 1 to Cohort 2 without interruption if none of the KAE609 arms in Cohort 1 meets the stopping criteria.

*Results from Cohort 1 and Cohort 2 will be analyzed to determine the safe and efficacious exposure range and the corresponding doses (KAE dose regimen 3) for participants in Cohorts 3 to 5.

Doses for Cohort 4 will be confirmed after PK analysis from upto 6 KAE609 participants from Cohort 3 and for Cohort 5, it would be post completion of Cohort 4 .

** Cohort 5 recruitment is dependent on availability of adequate toxicology package to dose down to ≥ 6 m

KAE609 doses across the study will be adaptive depending on the safe and efficacious exposure range identified before the study (for Cohorts 1-2) and after interim assessment of Cohort 1 & 2 (for Cohorts 3-5)

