4.2 Rationale for dose/regimen and duration of treatment

The primary aim of the intravenous antimalarial treatment in severe malaria is a rapid reduction of the initial parasite load. The efficacy of oral cipargamin in terms of parasite clearance has been demonstrated in previous studies using single doses between 10 mg and 150 mg. In study CKAE609A2202, aparasitemia was achieved by as early as 12 hours post-dose in the majority of the subjects treated with a single dose of oral cipargamin of ≥ 25 mg and by 24 hours post-dose in the majority of the subjects treated with oral cipargamin irrespective of dose. CCI

IV artesunate, the standard of care for severe malaria, has reported mean PRR₂₄ values between 7 and 43 across studies (Newton et al 2001, Nealon et al 2002, Newton et al 2003, Maude et al 2014). The CCI from four oral cipargamin studies including more than 150 participants with uncomplicated malaria (CKAE609X2201, CKAE609X2202, CKAE609A2201 and CKAE609A2202) is shown in Figure 4-1. In these studies, participants with baseline parasitemia of up to 60,000 parasites per μ l were included CCI oral cipargamin treatment. The full exposure-response relationship in participants with hyperparasitemia, as expected in severe malaria, remains to be elucidated.

In the same study CKAE609A2202, no safety concerns in patients with uncomplicated malaria were associated with CCI

The doses of IV cipargamin in this study have been selected in order not to exceed these mean exposures from the previous study.

The PK exposures of cipargamin following IV administration were predicted using a population PK model based on preliminary data from the first two cohorts of the ongoing phase 1 study CKAE609X2111. An adjustment in predicted exposures was made CCI (Silamut et al 1991) and the impact of CCI observed in studies in uncomplicated malaria and in healthy volunteers study, CCI CKAE609X2111.

Based on the above criteria, selected doses for Cohorts 1-2, i.e. 20 and 40 mg once every 24 hours, are expected to provide exposures within the safe and efficacious range. Due to the half-life of cipargamin of approximately 24 hours, cipargamin is expected to accumulate with daily

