The proportion of patients who were alive without new/worsening complication at the end of study for artesunate was 0.679 in SEQUAMAT and 0.791 in AQUAMAT (private communication). Therefore, it is estimated that the proportion of patients meeting the proposed clinical endpoint is about 0.75 in the artesunate arm. To date, cipargamin has not been tested in patients with severe malaria. It is assumed that the proportion in the cipargamin regimen would be same as that of artesunate.

From [Figure 3-2](#), a sample size of $n=107$ per regimen is required in order to have at least 80% probability that the half width of 2-sided 90% CIs for the difference between 2 proportions is at most 0.1 if the true proportion is 0.75 for both treatment groups. As patients treated with the same treatment from all cohorts will be pooled together for the analysis using the FAS, this sample size is considered for the artesunate and the cipargamin dose regimen that is used in all cohorts.

Taking account that about 8% patients may be excluded from the FAS, patients from all cohorts will be randomized to yield about 116 randomized each for the artesunate and the cipargamin dose regimen that is used in all cohorts so that 107 patients per group are evaluable for this analysis. The enrollment may be increased if the number of patients excluded from the FAS is higher. Considering the required sample size for each cohort for the primary endpoint (see [Section 3.1](#)) and the potential patient population available for recruitment, the 116 randomized for a treatment group will split into 6 patients for Cohort 1, 14 patients for Cohort 2, 38 patients for Cohorts 3 and 4, and 20 patients for Cohort 5.

Figure 3-2 Plot of probability that half width of 2-sided 90% CIs for 2 proportion difference is at most 0.1 for various true equal proportions

Generated using R 3.4.3.

Safety events

[figure not shown]
Safety events will be evaluated using the safety set, which is expected to be similar to the randomized set. Occurrence of a safety event for a regimen (cipargamin or artesunate) will be evaluated by cohort and overall with all patients pooled from all cohorts. The probability of observing selected minimal number of events is displayed in [Figure 3-3](#) by sample size. From this plot,

- for a treatment group in a cohort with 6 patients, the probability of observing at least 2 events is $> 75\%$ if true event rate is $\geq 40\%$ but $< 20\%$ if true event rate is $\leq 10\%$

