It has been observed in the Phase II study of oral KAE609 formulation for uncomplicated malaria that the most patients have achieved parasite clearance by 24 hours. This implies that post 24 hours results may be negative for all KAE609 patients, which results into a constant value for all the patients. For artesunate, the median parasite clearance time is expected to be >40 hours. Therefore, post 48 hours, results may be negative for all artesunate patients, which results into a constant value for all the patients. In such cases, variables with constant value will be dropped from imputation model, otherwise, SAS procedure, PROC MI will fail with error.

Clinical success at different visits will be imputed using discriminant function by FCS method. The imputations will be done separately for each treatment group. The number of imputations will be set to 100; the seed for the random function will be set to 60912201 for this study.

To generate the multiple imputed data sets, the SAS procedure MI can be used as follows:

The input data set <CLNSUC_dd> should have one record per patient with country, age, baseline weight, gender, log (parasite counts) from baseline up to 18 hours for KAE (and up to 48 hours for artesunate), parasitaemia status from 24 to 72 hours (presence/absence) for each visit for KAE609 (72 hours for artesunate), altered consciousness (yes/no) at each visit, renal impairment (yes/no) at each visit, acidosis (yes/no) at each visit, and clinical success (yes/no) at each visit.

Two outputs will be prepared displaying i) the missing data patterns and the group means as stored in the data set msgpat and ii) the variance information and estimated means with confidence interval and range based on data sets varinfo and param which need to be merged by <treatment group> and <variable>.

The imputed data are saved in data set <impdata>.

For each of the completed dataset, clinical success will be derived according the definition in [Section 2.1.1](#). The percentage of patients with clinical success (\hat{P}) at different timepoints such as 24 hours, 48 hours, 72 hours, hospital discharge, Day 6, Day 8, Day 15, Day 22, and Day 29 will be calculated as $n/N \times 100\%$ for each treatment group and for each of the complete datasets; where n =no. of patients with clinical success and N =no. of patients in FAS.

Combining clinical success rates and 90%CI for each treatment group

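### The 0.75 success rate behind the 107-per-arm precision claim is borrowed from a different endpoint, and the stated 80% probability is not assured at nearby rates

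*Protocol*

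**What the plan says.** Protocol 2.2 defines the key secondary variable as a binary outcome at 48 hours: "participant is alive and has absence of asexual parasites and no critical signs of severe malaria". Protocol Table 8-3 lists the key signs: altered consciousness including prostration, renal impairment, and acidosis or respiratory distress.

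Protocol 12.8.2 chooses the sample size so that, at a likely true rate, there is at least 80% probability that the half-width of the two-sided 90% interval for the difference is no more than 0.1. The rate comes from two earlier artesunate trials. In one, the share "alive without new/worsening complication at the end of study for artesunate was 0.679"; in the other it was 0.791, both by private communication. The next sentence is "Therefore, it is estimated that the proportion of participants meeting the proposed clinical endpoint is about 0.75 in the artesunate arm". For the test arm, "It is assumed that the proportion in the cipargamin arm would be same as that of artesunate". The result is 107 evaluable and 116 randomised per arm. SAP 3.2 carries the same derivation: "Therefore, it is estimated that the proportion of patients meeting the proposed clinical endpoint is about 0.75 in the artesunate arm".

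On artesunate clearance, protocol 4.2 reports mean 24-hour parasite reduction ratios (PRR24) with "values between 7 and 43 across studies". SAP 5.8.4 adds: "For artesunate, the median parasite clearance time is expected to be >40 hours". The same SAP section notes that most patients in the oral cipargamin study of uncomplicated malaria had cleared parasites by 24 hours.

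**The concern.** The borrowed outcome and the sized outcome differ in three ways. As described, the borrowed one has no parasite criterion. It does not require signs present at baseline to have resolved. It is read at end of study, not at 48 hours. Protocol 8.3.3 says the composite is being used for the first time, so a proxy was unavoidable, but the step from proxy to composite is asserted and not argued.

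Two things rest on it. The 107/116 figure and the precision statement are justified only at 0.75 in both arms. And protocol 12.8.2 says the endpoint may become the Phase III primary, so an unbridged 0.75 could be carried into the sizing of that trial.

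**Working it through.** **Method.** For each arm, the uncorrected Wilson limits with z = 1.645 are (p̂ + z²/2n ± z√[p̂(1−p̂)/n + z²/4n²]) / (1 + z²/n). The interval for the difference d = p̂₁ − p̂₂ is L = d − √[(p̂₁−l₁)² + (u₂−p̂₂)²] and U = d + √[(u₁−p̂₁)² + (p̂₂−l₂)²], as in SAP 2.5.2. The probability is the sum of Bin(x₁; n, p₁)·Bin(x₂; n, p₂) over all outcomes with (U−L)/2 ≤ 0.1. This is exact enumeration.

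**The plan's figures reproduce.** At 0.75 in both arms, n = 106 gives 79.0% and n = 107 gives 83.8%, so 107 is the smallest n that reaches 80%. At 0.5 in both arms the smallest n is 133, as stated.

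**Other rates, n = 107 per arm.** The simple mean of the two source rates is (0.679 + 0.791)/2 = 0.735.

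| Cipargamin | Artesunate | P(half-width ≤ 0.1) | Expected half-width |
|---|---|---|---|
| 0.75 | 0.75 | 83.8% | 0.097 |
| 0.735 | 0.735 | 68% | 0.098 |
| 0.70 | 0.70 | 26% | 0.102 |
| 0.679 | 0.679 | 9.6% | 0.104 |
| 0.50 | 0.50 | about 0% | 0.111 |
| 0.75 | 0.65 | 32% | 0.101 |
| 0.75 | 0.60 | 16% | 0.103 |
| 0.75 | 0.50 | 7% | 0.104 |
| 0.75 | 0.40 | 18% | 0.102 |
| 0.75 | 0.30 | 61% | 0.099 |
| 0.75 | 0.25 | 85.7% | 0.096 |
| 0.85 | 0.50 | 86.8% | 0.097 |

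The effect is not one-directional, because the variance is largest at 0.5 and falls again below it. With cipargamin at 0.85, 86.8% is the lowest value at any artesunate rate tried.

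**Is 0.75 consistent with the plan's clearance figures?** The documents give no 48-hour parasite-free share for artesunate, so these are rough checks under stated assumptions.

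- *PRR24, log-linear decline, local detection limit 10/µL (SAP 2.1.1).* The largest baseline cleared by 48 hours is 10 × PRR24². PRR24 = 43 gives 18,490/µL. PRR24 = 7 gives 490/µL, below the 5,000/µL entry minimum of Cohorts 2–5.
- *Median clearance time.* With a log-normal time, the share clear at 48 hours is Φ(ln(48/median)/σ). A median of 40 h, the bottom of the SAP's range, gives 82% to 64% for assumed σ of 0.2 to 0.5. A median of 44 h gives 67% to 57%.
- *The 45% with 90% reduction at 12 hours (protocol 12.8.1, SAP 3.1).* With an assumed SD of log₁₀ 12-hour reduction of 0.2 to 0.6, the share clear at 48 hours is 93% to 66% at a baseline of 5,000/µL, 60% to 50% at 50,000/µL, and 27% to 39% at 250,000/µL.

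Clinical success cannot exceed the parasite-free share, since key signs must also be absent. So 0.75 lies at or above the top of most of these ranges, but inside some of them.

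**The case against.** The strongest reply is that nothing is miscalculated. The 80% is stated on the condition that both true rates are 0.75, and it is correct there. Protocol 12.8.2 also discloses the dependence on the rate: it says n rises towards 0.5, gives 133 for that case, and plots rates from 0.5 to 0.9. All of this stands.

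A reader might infer that the clearance figures make 0.75 implausible. The documents do not support that. They give neither a baseline distribution nor a spread of clearance, and their figures disagree with one another: 45% at 12 hours implies a median PRR24 of roughly 70–90 under log-linear decline, not 7–43. The high baselines of 60,000–250,000/µL define Cohort 1 only, which is 6 of 116 per arm. At 5,000/µL, clearance by 48 hours needs a PRR24 of only √(5,000/10) ≈ 22. SAP 5.8.4 also allows that artesunate results after 48 hours may all be negative.

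A reader might also infer that the planned precision will not be delivered. That does not follow either. If artesunate success is very low, as a literal reading of PRR24 7–43 would suggest, or if cipargamin does very well, the 80% holds. If all 116 per arm are evaluable, the probability rises to 78.4% at 0.70/0.70 and 51.7% at 0.75 against 0.50.

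Finally, the low probabilities are partly a threshold effect: for 0.75 against 0.4–0.6 the expected half-width misses 0.100 by only 0.002–0.004. That limits the importance of the point but does not supply the missing bridge. Nor does a clearance argument have to be won: five percentage points less in both arms takes the probability from 84% to 26%, and one of the plan's own two source rates takes it to 9.6%.

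**Conclusion.** The concern holds in a limited form. The 0.75 is taken from a different outcome at a different time and is unsupported for the 48-hour composite. The plan's clearance figures make it doubtful without excluding it. The equal-rate assumption sits poorly with the faster clearance expected on cipargamin, although that expectation comes from oral dosing in uncomplicated malaria.

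The 80% statement is correct only at its stated condition. With cipargamin at 0.75 or equal to artesunate, it fails over roughly 0.25 to just under 0.75 for artesunate. The practical loss is modest, at most about 0.11 expected half-width at 107 per arm, and this is an estimation objective with no hypothesis test. The issue is the honesty of the stated precision and the benchmark passed to Phase III; it does not show that the trial is too small.

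The probabilities use the unstratified interval on which the plan sized the study. The planned analysis of the pooled difference is a Mantel-Haenszel estimate stratified by cohort, so they describe the sizing claim and not exactly the interval that will be reported.

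**What to change.** In protocol 12.8.2 and SAP 3.2:

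1. Stop deriving 0.75 for the 48-hour composite from the end-of-study complication rates.
2. State a justified 48-hour range for each arm, taking the parasite-free requirement into account and allowing the arms to differ. Do not keep 0.75 for cipargamin by default, since it has the same source. Label the rates as assumptions.
3. Replace the single 80% statement with a table of probability and expected 90% half-width at 107 per arm across that range, in the form of the table above.

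The cost is some wording and one recalculated table. Enrolment need not change. The downside is that the stated precision will look less favourable over much of the range.
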